11.1.3.5 Elevated Serum Creatinine

Subjects with increases in serum creatinine to $> 2 \times$ ULN should be evaluated for non-renal causes of renal dysfunction, such as dehydration due to diarrhea. Cystatin C values should also be utilized to evaluate renal function. Management of subjects without clinically likely non-renal causes of renal dysfunction should be discussed with the medical monitor.

11.1.3.6 Elevated Serum Amylase

In the event of asymptomatic increase of serum amylase to $> 1.5 \times$ ULN, lipase, fasting triglycerides, and amylase isoenzymes should be drawn. Further management should be discussed with the medical monitor.

11.1.3.7 Interstitial Lung Disease

Dyspnea in subjects in the study should be evaluated with chest X-ray or CT of the chest to determine whether interstitial lung disease is present. Tesevatinib should be discontinued if interstitial lung disease is suspected, and further management discussed with the medical monitor.

11.2 Study Drug Accountability and Subject Treatment Compliance

Drug accountability and subject treatment compliance will be assessed using drug dispensing and return records. The principal investigator is responsible for ensuring adequate accountability of all used and unused study drug. While the principal investigator may delegate components of drug accountability tasks to documented designee(s) (e.g. pharmacist), the ultimate responsibility for drug control and accountability resides with the investigator. This includes acknowledgment of receipt of each shipment of study drug (quantity and condition) and the maintenance of subject dispensing records and returned study product documentation. Dispensing records will document quantities received from Kadmon and quantities dispensed to subjects, including lot number, date dispensed, subject identification number, subject initials, and the initials of the person dispensing study drug. Reasons for deviation from the expected dispensing regimen also must be recorded.

At study initiation, the study monitor will evaluate and obtain a copy of each site's written standard operating procedure for study drug disposal/destruction in order to ensure that it complies with the requirements of Kadmon.

At the end of the study, following final drug inventory reconciliation by the monitor, the study site will dispose of and/or destroy any remaining unused study drug supplies, including empty containers, according to institutional procedures for destruction, reviewed and approved by Kadmon prior to material destruction. If the site cannot meet the requirements of Kadmon for disposal, arrangements will be made between the site and Kadmon or its representative, for destruction or return of unused study drug supplies.

All drug supplies and associated documentation will be periodically reviewed and verified by the study monitor over the course of the study.

12 CONCOMITANT MEDICATION AND TREATMENT

If the subject must use a concomitant medication during the study, it is the responsibility of the principal investigator to ensure that details regarding the medication are recorded on the eCRF.

Subjects should avoid ingesting grapefruit, pomelo or Seville orange fruits (and juice) with tesevatinib or at any time during the study. Subjects should not take medications that are associated with a risk of QTc(F) interval prolongation and/or torsades de pointes. Additionally, subjects are not permitted to take concomitant medications that moderately or severely inhibit (e.g. ketoconazole, itraconazole, erythromycin, clarithromycin) or induce (e.g. phenytoin, carbamazepine, rifampicin, or phenobarbital) the CYP3A4 isozyme. Steroid medications are allowed.

Administration of acid-reducing medications should be avoided during the study as these agents may decrease exposure to tesevatinib. If acid-reducing agents are needed, H-2 antagonists or antacids will be recommended rather than proton pump inhibitors. Administration of acid-reducing agents such as H-2 antagonists or antacids, if required, should take place no less than 2 hours before or after dosing with tesevatinib.

Since tesevatinib is a potent inhibitor of MATE transporter proteins, increased levels of concomitant medications that are secreted by the kidney proximal tubule cells into the renal tubule by MATE transporter proteins may occur. Thus subjects taking cephalexin, cimetidine, dofetilide, fexofenadine, metformin, procainamide, and pyrimethamine should be monitored carefully.

Other prohibited treatments include the following:

- Other investigational drugs;
- Concurrent anti-tumor therapies such as chemotherapy, gene therapy, biologics, radiation therapy, or other immunotherapy;
- Medications known to moderately or severely inhibit the CYP3A4 isozyme or any drugs that are moderate or severe CYP3A4 inducers. A stable regimen (≥ 4 weeks) of antidepressants of the SSRI class is allowed (common SSRIs include escitalopram oxalate, citalopram, fluvoxamine, paroxetine, sertraline, and fluoxetine) ;

- Drugs associated with torsades de pointes or known to prolong the QTc interval, including anti-arrhythmic medications within 2 weeks prior to Day 1 of treatment on study.

Antiemetics and antidiarrheal medications should not be administered prophylactically before initial treatment with study drug. At the discretion of the investigator, treatment of symptoms with antiemetic and antidiarrheal medications may be undertaken per standard clinical practice.

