12.3 Interaction of Tesevatinib with Other Medications

Microsomal oxidation of tesevatinib involves CYP3A4; the percentage conversion of tesevatinib in human microsomes was low. This suggests a low potential for other drugs to significantly affect the biotransformation of tesevatinib in humans through interaction with CYP3A4-mediated metabolic pathways.

In vitro studies have indicated that tesevatinib has a moderate potential to inhibit the CYP2C8 family of liver enzymes. This inhibition, should it occur clinically, could increase exposure to other drugs that are substrates for this pathway. However, the inhibition of CYP2C8, CYP2C9 and CYP2C9*2 in enzyme assays required tesevatinib levels of 7–9 μM . These levels are well above plasma concentrations achievable in vivo at the doses proposed in this study.

Although not expected to be an issue, inhibitors, inducers, and substrates of CYP2C8, CYP2D6, and CYP1A2 should be avoided in all subjects while receiving study drug. These medications should be used with caution and discussed with the medical monitor prior to use. In addition, subjects must be closely monitored for the desired drug effect and potential AE.

See Appendix D for a list of drugs that are substrates, inhibitors, and inducers of CYP3A4, CYP2C8, CYP2D6, and CYP1A2.

12.3.1 Management of Subjects Requiring Concomitant Medications Associated with QT Interval Prolongation

Tesevatinib has been associated with prolongation of the QT interval. Subjects requiring treatment with drugs known to be associated with torsades de pointes or significant QT interval prolongation may not be enrolled into this study. This includes Class IA antiarrhythmics (e.g. quinidine, procainamide); Class III antiarrhythmics (e.g. amiodarone, sotalol, dofetilide); phenothiazine anti-psychotics: (e.g. chlorpromazine, mesoridazine, pimozide, thioridazine); quinolone antibiotics: (e.g. gatifloxacin, moxifloxacin, sparfloxacin); macrolide antibiotics (e.g. erythromycin, clarithromycin, and troleandomycin) and other drugs that have a contraindication or boxed warning regarding QT prolongation in the prescribing information.

Appendix E, Concomitant Medications Associated With a Risk of QTc(F) Interval Prolongation and/or Torsades de Pointes, contains a partial list of drugs associated with a risk of QT interval prolongation and/or torsades de pointes.

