APPENDIX D: CONCOMITANT DRUGS THAT SHOULD BE USED WITH CAUTION*

Use of drugs that are substrates of the CYP3A4/5 family should be with caution in subjects who are receiving tesevatinib if deemed clinically necessary and the subject can be closely monitored for the desired drug effect and potential AEs. The following drugs induce or are a substrate for CYP3A4/5. **This list is not comprehensive, and all concomitant medications should be evaluated for possible interactions with tesevatinib.**

Drug Type	Drug Names
Anti-arrhythmics	quinidine**
Anti-epileptics	carbamazepine, phenytoin, phenobarbital
Antihistamines	astemizole, chlorpheniramine
Benzodiazepines	alprazolam, diazepam, midazolam, triazolam
Calcium channel blockers	amlodipine, felodipine, lercanidipine, nifedipine, nisoldipine, nitrendipine
Central nervous system depressants	barbiturates
HMG CoA reductase inhibitors	atorvastatin, cerivastatin, lovastatin, simvastatin
Immune modulators	cyclosporine, tacrolimus
Miscellaneous	amodiaquine, repaglinide, rifampin, torsemide, St John's Wort
Neuro-psychotropics	bupirone, haloperidol, methadone, pimozide
Steroids	estradiol, hydrocortisone, progesterone, testosterone

Reference: <http://medicine.iupui.edu/flockhart/table.htm>

HMG CoA, hydroxyl-methylglutaryl coenzyme A.

*Should be discussed with medical monitor

**Drugs that must be avoided per Appendix F, Concomitant Medications Associated With a Risk of QTc Interval Prolongation and/or Torsades de Pointes

Use of drugs that are substrates of the CYP2D6 also should be with caution in subjects who are receiving tesevatinib if deemed clinically necessary and the subject can be closely monitored for the desired drug effect and potential AEs.

Substrates of CYP2D6			
Amitriptyline	Doxepin	Methylphenidate	Propranolol
Amoxapine	Doxorubicin	Metoprolol	Protriptyline
Aripiprazole	Duloxetine	Mexiletine	Risperidone
Atomoxetine	Flecainide	Mirtazapine	Sertraline
Betaxolol	Fluoxetine	Moclobemide	Tamoxifen
Captopril	Fluphenazine	Nefazodone	Tamsulosin
Carvedilol	Fluvoxamine	Nortriptyline	Thioridazine
Chloroquine	Haloperidol	Oxycodone	Timolol
Chlorpromazine	Hydrocodone	Paroxetine	Tolterodine
Clomipramine	Imipramine	Perphenazine	Tramadol
Codeine	Labetalol	Pindolol	Trimipramine
Desipramine	Lidocaine	Pipotiazine	Venlafaxine
Dextroamphetamine	Lomustine	Procainamide	Zuclopenthixol
Dextromethorphan	Maprotiline	Promethazine	
Dihydrocodeine	Methamphetamine	Propafenone	

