In addition, use of drugs that are CYP1A2 inducers and inhibitors should be with caution in subjects who are receiving tesevatinib if deemed clinically necessary and the subject can be closely monitored for the desired drug effect and potential AEs.

CYP1A2 Inducers	CYP1A2 Inhibitors	
Barbiturates Carbamazepine (e.g. Tegretol) Primidone Rifampin (e.g. Rifadin)	Artemisinin Atazanavir (Reyataz) Cimetidine (Tagamet) Ciprofloxacin (Cipro) Enoxacin Ethinyl Estradiol Fluvoxamine	Mexiletine Tacrine (Cognex) Thiabendazole Zileuton (Zyflo)

Concomitant Drugs That Should Be Used with Extreme Caution*

Use of drugs that are inhibitors of the CYP3A4/5 family should be with caution in subjects who are receiving tesevatinib if deemed clinically necessary and the subject can be closely monitored for the desired drug effect and potential AEs. The following drugs are inhibitors of the CYP3A4/5 family. Use of these drugs may alter the pharmacokinetics of the study drug. **This list is not comprehensive, and all concomitant medications should be evaluated for possible interactions with tesevatinib.**

Drug Type	Drug Names
Anti-arrhythmics	amiodarone**
Antibiotic	norfloxacin, trimethoprim
Antidepressant	fluvoxamine, nefazodone, norfluoxetine
Antiemetic	Aprepitant
Antifungal medications	fluconazole, itraconazole, ketoconazole
Calcium channel blockers	diltiazem, verapamil
Macrolide antibiotics	clarithromycin* , erythromycin* , telithromycin
Miscellaneous	cimetidine, gemfibrozil, montelukast, quercetin, grapefruit juice
Oral hypoglycemic agents	Glitazones

*Should be discussed with medical monitor first

**Drugs that must be avoided per Appendix F, Concomitant Medications Associated with a Risk of QTc Interval Prolongation and/or Torsades de Pointes

APPENDIX E: CONCOMITANT MEDICATIONS ASSOCIATED WITH A RISK OF QTc(F) INTERVAL PROLONGATION AND/OR TORSADES DE POINTES

Use of these drugs should be avoided in subjects who are receiving tesevatinib unless deemed clinically necessary. Discuss with medical monitor the appropriate monitoring of subjects while receiving any of these drugs in conjunction with tesevatinib. Subjects should be closely monitored for QTc(F) prolongation and potential AEs. **This list is not comprehensive and all concomitant medications should be evaluated for potential contribution to QTc(F) prolongation. Refer to the following web site for additional listings and information:**

<https://crediblemeds.org/index.php?rf=US>

Drug Type	Drug Name

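### Section 12 prohibits eight named CYP3A4 inhibitors and inducers, Appendix D lists all eight for use with caution, and no text says which prevails

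*Protocol*

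**What the plan says.** Section 12 is worded as a prohibition: "subjects are not permitted to take concomitant medications that moderately or severely inhibit" CYP3A4, or that induce it. The inhibitors given as examples are ketoconazole, itraconazole, erythromycin and clarithromycin. The inducers are phenytoin, carbamazepine, rifampicin and phenobarbital. The list of other prohibited treatments in Section 12 repeats the ban by class. The synopsis row on prohibited treatments and the exclusion criteria for all three cohorts carry the class ban too.

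Section 12.3 then directs the reader elsewhere: "See Appendix D for a list of drugs that are substrates, inhibitors, and inducers of CYP3A4" and three other enzymes. The title of Appendix D concerns drugs to be used with caution, with a footnote to discuss them with the medical monitor. Its first table is introduced by "The following drugs induce or are a substrate for CYP3A4/5" and includes "carbamazepine, phenytoin, phenobarbital" and "amodiaquine, repaglinide, rifampin, torsemide". Its inhibitor table stands under "Concomitant Drugs That Should Be Used with Extreme Caution", opens with "Use of drugs that are inhibitors of the CYP3A4/5 family should be with caution in subjects who are receiving tesevatinib if deemed clinically necessary", and includes "fluconazole, itraconazole, ketoconazole" as well as clarithromycin and erythromycin. A separate table of CYP1A2 inducers, again for cautious use where clinically necessary, lists barbiturates, carbamazepine and rifampin.

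**The concern.** For any of these drugs started during treatment, one part of the protocol says no and another says possibly, after a conversation with the medical monitor. The exclusion criteria do not settle this, because they govern what a subject takes at entry and not what is started in a later cycle. Such a start is foreseeable. Section 5.3.1 notes that brain metastases can present with seizures, and three of the eight drugs are anti-epileptics.

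What is at stake is safety handling and exposure. The synopsis rests the ban on tesevatinib being metabolized largely by CYP3A4. Section 5.2.1 reports that QTc(F) prolongation rose with plasma concentration. In the earlier NSCLC study at 300 mg daily, which is this trial's dose, 2 of 41 subjects had centrally confirmed QTc(F) above 500 msec (Section 5.1.2). The conflict also leaves it unclear whether such a start would belong in the SAP's listing of protocol deviations.

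**Working it through.** No figure in the plan is involved, so the check is a comparison of lists. It uses the drugs named in Section 12 and the tables of Appendix D, and treats rifampicin and rifampin as one drug.

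| Drug in Section 12 | Banned as | Where in Appendix D | Basis for reading it as usable |
|---|---|---|---|
| ketoconazole | inhibitor | inhibitor table, extreme caution | explicit sentence above the table |
| itraconazole | inhibitor | inhibitor table, extreme caution | explicit sentence above the table |
| erythromycin | inhibitor | inhibitor table, extreme caution | explicit sentence above the table |
| clarithromycin | inhibitor | inhibitor table, extreme caution | explicit sentence above the table |
| carbamazepine | inducer | first table, caution; CYP1A2 table | explicit in the CYP1A2 text |
| rifampicin | inducer | first table, caution (as rifampin); CYP1A2 table | explicit in the CYP1A2 text |
| phenobarbital | inducer | first table, caution; within barbiturates in the CYP1A2 table | explicit in the CYP1A2 text, through the class name |
| phenytoin | inducer | first table, caution | heading and footnote only |

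Section 12 names 4 + 4 = 8 drugs, and all 8 are in Appendix D. Permission is explicit for 4 inhibitors + 2 inducers by name + 1 inducer by class = 7. The remaining one, phenytoin, is listed without an explicit permission. In the first table the sentence about clinical necessity governs CYP3A4/5 substrates. It does not mention inducers, which is why that table alone is weaker evidence.

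Two related texts bear on the repair.

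1. Erythromycin and clarithromycin are also QT drugs. Section 12.3.1 bars enrolment of subjects who need such drugs. It and Appendix E then allow an exception on study where the drug is judged clinically necessary. Section 12.3.1 also has a separate rule for a short course of at most 21 days, during which study drug is withheld.
2. The scope of the inducer ban differs. It covers any inducer in seven places: the synopsis exclusion criteria for three cohorts (3), the synopsis row on prohibited treatments (1), and Sections 8.3, 8.5 and 8.7 (3). Section 12 limits it to moderate or severe inducers.

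Neither document says which text prevails where they differ.

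**The case against.** The best reply is that the practical risk is already contained. Appendix D sends the site to the medical monitor, Section 12.1 requires that monitor's approval for additional therapeutic treatment, and subjects on these drugs at entry are excluded. Sections 9.1.8 and 11.1.3.4 provide ECG monitoring and QTc(F) rules. Section 12.3 itself infers a low potential for interaction through CYP3A4. All of this stands and limits the importance of the point. It does not remove the contradiction: a general approval step creates no exception to a ban, and a monitor working from Appendix D could approve what Section 12 forbids.

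A reader might infer more than the documents support, in four ways.

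- *Appendix D openly permits all eight drugs alike.* It does not. For phenytoin the inference rests on a heading and a footnote.
- *The eight are usable because none carries Appendix D's mark for drugs that must be avoided.* That mark refers only to the QT list. Six of the eight are not on that list, so no mark would be expected. For the two macrolides, the argument depends on counting asterisks in text read from a PDF.
- *The synopsis sentence letting the investigator give medication needed for the subject's welfare overrides the ban.* The prohibited-treatments row that follows it arguably limits it.
- *The wider inducer scope is the correct one.* It is the more frequent wording, but the documents give no reason to prefer it.

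**Conclusion.** The contradiction is real. All 8 drugs that Section 12 names as prohibited appear in Appendix D for use with caution or extreme caution; the conflict is explicit for 7 and implied for 1. This rests on taking rifampin as rifampicin and on barbiturates including phenobarbital. The consequence is that a site could follow the appendix in good faith and start a prohibited drug, with a possible effect on tesevatinib exposure and QTc(F). The documents give no size for that effect, and Section 12.3 suggests that it may be small. A reader might infer that the efficacy results are compromised. Nothing supports that: no SAP estimate, sample size or analysis changes. The correction should be made because it is a safety instruction that contradicts itself and is cheap to repair.

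**What to change.** 1. In Section 12 and at the head of Appendix D, state that drugs prohibited in Section 12 as moderate or severe CYP3A4 inhibitors or inducers may not be used with tesevatinib. State that Section 12 prevails over every listing of such a drug in Appendices D and E, including the CYP1A2 table and the entry for barbiturates as it covers phenobarbital. The named drugs are only examples of a class ban, so this sentence does most of the work.
2. Mark the eight named drugs in Appendix D as *Prohibited per Section 12*.
3. Keep the allowances for steroids and for an SSRI regimen stable for at least 4 weeks. Fluvoxamine is in Appendix D's inhibitor table, so the precedence sentence could otherwise be read as withdrawing that allowance.
4. For erythromycin and clarithromycin, state that the exception for clinical necessity in Section 12.3.1 and Appendix E does not permit use together with tesevatinib. Say that the existing rule for a short course with study drug withheld stays in force.
5. The sponsor should choose one scope for the inducer ban, either any inducer or moderate and severe ones, and use it throughout.
6. Clerical: the Appendix D footnotes cite Appendix F for the QT list, which is Appendix E.

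The cost is wording in Section 12, Section 12.3.1 and Appendices D and E. If the narrower inducer scope is chosen, the synopsis and Sections 8.3, 8.5 and 8.7 change too. There is no cost in data collection, sample size or analysis.

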12.1 Additional Therapy

A subject should not receive additional therapeutics treatment during the study period without the approval of the sponsor's medical monitor.

12.2 Additional Anti-Cancer Treatment and Radiotherapy

Subjects should not receive additional therapeutic anti-cancer treatment until after progressive disease (PD) has been documented on study and End of Treatment study assessments have been completed. If a subject requires additional anti-cancer treatment, study treatment will be discontinued and the subject will enter the Post-Treatment Period and followed every 8 weeks by phone call. However, subjects with limited peripheral disease progression (oligoprogressive disease) may receive local ablative treatment (radiation therapy or surgery) and then be continued on tesevatinib. Any such patients will be considered to have disease progression at the time of detection of oligoprogressive disease.

12.3 Interaction of Tesevatinib with Other Medications

Microsomal oxidation of tesevatinib involves CYP3A4; the percentage conversion of tesevatinib in human microsomes was low. This suggests a low potential for other drugs to significantly affect the biotransformation of tesevatinib in humans through interaction with CYP3A4-mediated metabolic pathways.

In vitro studies have indicated that tesevatinib has a moderate potential to inhibit the CYP2C8 family of liver enzymes. This inhibition, should it occur clinically, could increase exposure to other drugs that are substrates for this pathway. However, the inhibition of CYP2C8, CYP2C9 and CYP2C9*2 in enzyme assays required tesevatinib levels of 7–9 μM . These levels are well above plasma concentrations achievable in vivo at the doses proposed in this study.

Although not expected to be an issue, inhibitors, inducers, and substrates of CYP2C8, CYP2D6, and CYP1A2 should be avoided in all subjects while receiving study drug. These medications should be used with caution and discussed with the medical monitor prior to use. In addition, subjects must be closely monitored for the desired drug effect and potential AE.

See Appendix D for a list of drugs that are substrates, inhibitors, and inducers of CYP3A4, CYP2C8, CYP2D6, and CYP1A2.

12.3.1 Management of Subjects Requiring Concomitant Medications Associated with QT Interval Prolongation

Tesevatinib has been associated with prolongation of the QT interval. Subjects requiring treatment with drugs known to be associated with torsades de pointes or significant QT interval prolongation may not be enrolled into this study. This includes Class IA antiarrhythmics (e.g. quinidine, procainamide); Class III antiarrhythmics (e.g. amiodarone, sotalol, dofetilide); phenothiazine anti-psychotics: (e.g. chlorpromazine, mesoridazine, pimozide, thioridazine); quinolone antibiotics: (e.g. gatifloxacin, moxifloxacin, sparfloxacin); macrolide antibiotics (e.g. erythromycin, clarithromycin, and troleandomycin) and other drugs that have a contraindication or boxed warning regarding QT prolongation in the prescribing information.

Appendix E, Concomitant Medications Associated With a Risk of QTc(F) Interval Prolongation and/or Torsades de Pointes, contains a partial list of drugs associated with a risk of QT interval prolongation and/or torsades de pointes.

Drugs associated with QT interval prolongation should be avoided in subjects receiving study drug unless deemed clinically necessary. Should a subject develop a condition for which a medication known to affect QT interval is indicated, consideration should be given to the additive risk of QT interval prolongation versus the potential benefit of treatment with the required medication and/or study drug. Contact the medical monitor prior to the administration of the concomitant medication.

During long-term follow-up, subjects who require short-term (2 to 3 weeks, not to exceed 21 days) treatment with a concomitant medication associated with QT interval prolongation while receiving study drug should have the study drug withheld until the concomitant treatment course is complete. The decision about whether the subject can continue on trial following this interruption will be determined by the medical monitor.

During long-term follow-up, subjects who require chronic treatment with a concomitant medication associated with QT interval prolongation while receiving study drug should be monitored as follows:

- Three ECGs should be obtained prior to start of the concomitant medication. These ECGs should be obtained within a total span of 30 minutes with an interval of approximately 1–2 minutes between recordings;

- If the average QTc(F) interval from these 3 ECGs is > 60 msec above the average Cycle 1 Day 1 (Day 1 predose) value or is ≥ 500 msec, study drug may be discontinued or dose reduced after discussion with the medical monitor;
- If both of the above criteria are not met (i.e., the average QTc[F] interval is no more than 60 msec above Cycle 1 Day 1 and is < 500 msec), ECGs should be obtained daily for the first 3 days of treatment with the concomitant medication;
- Additionally, an ECG should be obtained weekly for 2 weeks, then every 2 weeks for 1 month and monthly thereafter until the concomitant medication is no longer required or study drug is discontinued.

QTc(F) interval prolongation should be managed as noted in Section 11.1.3.3.

